Pregnancy testing	X	-	X	-	-	-	-	X	Serum pregnancy test at screening; urine pregnancy test at all subsequent time points.
FSH testing	X	-	-	-	-	-	-	-	FSH of 2.25 U/mL must be documented to confirm post-menopausal status in female participants who have had at least 12 months without menses.
Research samples/ Central laboratory									
Blood PK sampling	-	-	X	X	X	X	X	X	Blood sample for PK concentrations collected predose on Day 0 only; 4min (+/- 1 min) postdose on Days 0, 7, and 14.
Antidrug antibodies	-	-	X	-	-	-	-	X	Predose on Day 0.

Procedures	Screening Period	Prior to Rand	Rand/ Baseline	Treatment Period				End of Study/ Final Safety	Notes
Visit	V -1	V0	V1	V2	V3	V4	V5	V6	
Week	-6	-	0	1	2	4	6	8	
Day	-	-	0	7	14	28	42	56	
Window	≤ 6 weeks	-	-	± 3 days	± 3 days	± 3 days	± 3 days	± 3 days	
Biopsies for central lab	X	-	-	-	X			-	Screening endoscopy with esophageal biopsies and photographs are to be performed during screening period to allow results to be available prior to Visit 1.
Central histology result received prior to visit	-	X	-	-	-	-	-	-	
Whole blood for PBMC: Immune cell phenotyping (T, B, & Mo-subsets) and A20	X	-	X	X	X	X	X		Predose and 2 hours (+/- 10 minutes) postdose on Days 0, 7, and 14.
Serum cytokines	X	-	X	X	X	X	X	X	Predose and 2 hours (+/- 10 minutes) postdose on Days 0, 7, and 14.
Serum IgE/IgG4 (total)	X	-	X	X	X	X	X	X	Predose and 2 hours (+/- 10 minutes) postdose on Days 0, 7, and 14.
Serum EDN	X	-	X	X	X	X	X	X	Predose and 2 hours (+/- 10 minutes) postdose on Days 0, 7, and 14.

Base = baseline; DSQ = Dysphagia Symptom Questionnaire; ECG = electrocardiogram; EDN = eosinophil derived neurotoxin; EDP = EoE diagnostic panel; EGD = esophagogastroduodenoscopy; EoE = eosinophilic esophagitis; EoEHSS = EoE Histology Scoring System; EREFS = Endoscopic Reference Score; d = days; FSH = follicle stimulating hormone; FU = follow-up; Ig = immunoglobulin; IWRs = Interactive Web Response System; IV = intravenous; Mo = macrophage; q2wk = once every 2 weeks; PBMC = peripheral blood mononuclear cell; PGI-C = Patient Global Impression of Change; PGI-S = Patient Global Impression of Severity; PK = pharmacokinetic; QoL = quality of life; Rand = randomization; DBL = double-blind; Screen = screening; TBD = to be determined; V = visit

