26. Any other medical or psychological condition including relevant laboratory abnormalities at screening that, in the opinion of the investigator, suggest a new and/or insufficiently understood disease, may present an unreasonable risk to the participant as a result of his/her participation in this clinical study, may make the participant's participation unreliable, or may interfere with study assessments. The specific justification for participants excluded under this criterion will be noted in study documents (eg, chart notes, electronic case report form). These may include participant-reported alcohol or drug abuse and severe concomitant illness(es).
27. Planned or anticipated use of any prohibited medications and procedures (as described in the exclusion criteria) during study treatment.
28. Treatment with a live (attenuated) vaccine within 3 months prior to screening and/or treatment of a killed vaccine within 30 days prior to screening, until the end of the study with the exception of a coronavirus disease of 2019 (COVID-19) vaccine, as described in Section 9.2.1.
29. Pregnant or breastfeeding women, or women planning to become pregnant or breastfeed during the study.
30. Women unwilling to use adequate birth control, if of reproductive potential* and sexually active. Adequate birth control is defined as agreement to consistently practice an effective and accepted method of contraception throughout the duration of the study and for 30 days after the last dose of study treatment. These include: hormonal contraceptives, intrauterine device, or double barrier contraception (ie, condom and diaphragm), or male partner with documented vasectomy.

*For females, menopause is defined as at least 12 consecutive months without menses; to include laboratory confirmation of post-menopausal status (ie, a follicle stimulating hormone (FSH) of 2.25 U/mL must be documented). Hysterectomy, bilateral

oophorectomy, or bilateral tubal ligation must be documented, as applicable; if documented, women with these conditions are not required to use additional contraception.

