8.3.2. Individual Stopping Criteria

Participants will be permanently discontinued from study treatment in the event of:

- Anaphylactic reaction to study treatment
- Treatment with any prohibited concomitant medication or procedure (Section 9.2.2)
- Diagnosis of a malignancy during study, excluding carcinoma in situ of the cervix or squamous or basal cell carcinoma of the skin
- Evidence of pregnancy
- Any infection that:
 - Requires parenteral treatment with antibiotic, antifungal, antiviral, anti-parasitic, or anti-protozoal agent
 - Requires oral treatment with such agents for longer than 2 weeks
 - Is opportunistic, such as tuberculosis and other infections whose nature or course may suggest an immunocompromised status
- Severe laboratory abnormalities, such as:
 - Neutrophil count $<0.5 \times 10^3/\mu\text{L}$
 - Platelet count $<50 \times 10^3/\mu\text{L}$
 - ALT and/or AST values $>3 \times \text{ULN}$ with total bilirubin $>2 \times \text{ULN}$, excluding confirmed Gilbert's Syndrome
- Confirmed AST and/or ALT $>5 \times \text{ULN}$ (for more than 2 weeks)
- Other reasons that may lead to the permanent discontinuation of study treatment include:

- Certain AEs deemed related to the study treatment (eg, severe and prolonged injection site reactions) or study procedures

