12.5. Laboratory Assessments

Detailed instructions for blood sample collection are in the study manuals provided to study centers.

Local Laboratory Assessments:

The following clinical laboratory parameters will be assessed:

Blood Chemistry

Sodium	Total protein, serum	Total and indirect bilirubin
Potassium	Creatinine	Total cholesterol
Chloride	Blood urea nitrogen	Low-density lipoprotein
Carbon dioxide	AST	High-density lipoprotein
Calcium	ALT	Triglycerides
Glucose	Alkaline phosphatase	Uric acid
Albumin	Lactate dehydrogenase	CPK

Hematology

Hemoglobin	Differential:
Hematocrit	Neutrophils
Red blood cells	Lymphocytes
White blood cells	Monocytes
Red cell indices	Basophils
Platelet count	Eosinophils

Urinalysis

Microscopic analysis will only be done in the event of abnormal dipstick results.

Color	Glucose	Red blood cells
Clarity	Blood	Hyaline and other casts

pH	Bilirubin	Bacteria
Specific gravity	Leukocyte esterase	Epithelial cells
Ketones	Nitrite	Crystals
Protein	White blood cells	Yeast

Serological markers

HIV-1/2 antibodies	HBsAg	Hepatitis C virus antibodies
--------------------	-------	------------------------------

Other laboratory tests:

- Serum pregnancy tests will be performed for females of reproductive potential at screening, after which urine pregnancy tests will be performed.
- FSH testing will be performed at screening to confirm post-menopausal status in female participants who have had at least 12 months without menses.
- Coagulation testing (prothrombin time and partial thromboplastin time) will be performed as indicated in the Schedule of Events ([Table 3](#)). Samples for coagulation tests should be obtained before the procedures of endoscopy with esophageal biopsies are performed.

Abnormal laboratory values and laboratory AEs:

- All laboratory values must be reviewed by the investigator or authorized designee.
- Significantly abnormal tests must be repeated to confirm the nature and degree of the abnormality. When necessary, appropriate ancillary investigations should be initiated. If the abnormality fails to resolve or cannot be explained by events or conditions unrelated to the study treatment or its administration, the medical monitor must be consulted.
- The clinical significance of an abnormal test value, within the context of the disease under study, must be determined by the investigator.

Criteria for reporting laboratory values as an AE are provided in Section [12.6.1.4](#).

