12.6.1.3. Other Adverse Events

The following events require reporting to the sponsor (or designee) within 24 hours of learning of the event:

Pregnancy

Should a pregnancy occur, it must be reported and recorded on the sponsor's pregnancy form. Pregnancy in itself is not regarded as an AE unless there is a suspicion that an investigational product may have interfered with the effectiveness of a contraceptive medication.

Although pregnancy is not considered an AE, it is the responsibility of the investigator to report to the sponsor (or designee) by telephone within 24 hours of identification, any pregnancy occurring in a female participant or female partner of a male participant, during the study or within 120 days of the last dose of study treatment. Any complication of pregnancy affecting a female study participant or female partner of a male study participant, and/or fetus, and/or newborn must be reported as an SAE.

The outcome of all pregnancies (spontaneous miscarriage, elective termination, normal birth, or congenital abnormality) must be followed up and documented even if the participant was discontinued from the study.

Overdose of Study Treatment

Any accidental or intentional overdose over the intended dose of study treatment within the intended therapeutic window, if associated with an AE, should be reported within 24 hours.

Adverse Events of Special Interest

Adverse events of special interest (AESIs) must be reported within 24 hours of identification. Adverse events of special interest in this study include:

- Anaphylactic reactions or acute allergic reactions that require immediate treatment
- Severe injection site reactions that last longer than 24 hours
- Any severe infection, any bacterial infection requiring treatment with parenteral antibiotics or treatment with oral antibiotics for longer than 2 weeks, any clinical endoparasitosis, any opportunistic infection, any viral infection requiring antiviral treatment
- Note: Generally, all uncommon, atypical, peculiar, or unusually persistent infections, especially viral infections, should be reported as AESI.

Refer to the study manuals for the procedures to be followed.

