TEAEs will be summarized by treatment, system organ class, preferred term and relationship to the study treatment is recorded as related (definitely, probably, and possibly) and unrelated (unlikely and not related). The number (%) of participants having relationship for each event and the number of events will be presented.

All AEs (including non-TEAEs) recorded on the CRF will be listed.

Adverse Events of Special Interest

A summary of the frequency (number and percentage of participants) of AESIs will be presented by SOC, PT and Listed separately.

Serious Adverse Events

SAEs and treatment related SAEs will be summarized separately by SOC and PT. All SAEs recorded on the CRF will be listed for all participants.

Adverse Events Leading to Study Drug Discontinuation

All AEs leading to discontinuation recorded on the CRF will be listed.

Deaths

Deaths occurring in the study will be listed for all participants.

Clinical Laboratory Data

The Clinical Laboratory test category will include the following assessments:

Hematology: Hemoglobin, Hematocrit, Red blood cells count, white blood cell count, red cell indices, Platelet count and differential (neutrophil, lymphocyte, monocyte, eosinophil, and basophil). Visits include screening, Day 0, Day 7, Day 56.

Biochemistry: Sodium, Total protein, Total and indirect bilirubin, Potassium, Creatinine, Total cholesterol, Chloride, Blood urea nitrogen, Low-density lipoprotein, Carbon dioxide, AST, High-density lipoprotein, Calcium, ALT, Triglycerides, Glucose, Alkaline phosphatase, Uric acid, Albumin, Lactate dehydrogenase, CPK. Visits include screening, Day 0, Day 7, Day 56.

Coagulation: Prothrombin time and partial thromboplastin time. Visits include screening, Day 0, Day 7, Day 56.

Urinalysis: Color, Glucose, Red blood cells, Clarity, Blood, Hyaline and other casts, pH, Bilirubin, Bacteria, Specific gravity, Leukocyte esterase, Epithelial cells, Ketones, Nitrite, Crystals, Protein, White blood cells, Yeast. Visits include screening, Day 0, Day 7, Day 56.

Serology: HIV-1/2 antibodies, HBsAg Hepatitis, C virus antibodies. Collecting at screening visit only.

Pregnancy: Serum pregnancy tests will be performed for females of reproductive potential at screening, after which urine pregnancy tests will be performed. Visits include screening, Day 0 and Day 56.

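### Pregnancy permanently stops treatment, but after Day 0 the next scheduled pregnancy test is on Day 56, so no scheduled test after Day 0 can stop dose 2 or dose 3 (minor; cheap to improve)

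*Protocol*

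**What the plan says.** Protocol 8.3.2 opens its list of individual stopping criteria with "Participants will be permanently discontinued from study treatment in the event of", and one item on the list is "Evidence of pregnancy". Protocol 7.1 sets the doses at Days 0, 7 and 14.

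In Protocol 7.9, Table 3, the pregnancy-testing row is marked at screening, Day 0 and Day 56, with dashes at every visit between Day 0 and Day 56. The row's note says "Serum pregnancy test at screening; urine pregnancy test at all subsequent time points". The SAP's copy of the schedule (SAP 2.2) carries the same marks and note. SAP 7.8 states the visits outright: "Visits include screening, Day 0 and Day 56". Protocol 12.5 describes the tests without naming visits for the urine tests: "Serum pregnancy tests will be performed for females of reproductive potential at screening, after which urine pregnancy tests will be performed".

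The surrounding safeguards are these. Exclusion 29 bars pregnant women and those planning pregnancy. Exclusion 30 requires an "effective and accepted method of contraception throughout the duration of the study and for 30 days after the last dose of study treatment". Section 12.6.1.3 makes any pregnancy reportable if it occurs "during the study or within 120 days of the last dose of study treatment". Table 3 marks urinalysis at Days 7 and 14.

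**The concern.** A stopping rule that guards against further exposure works best when something scheduled can trigger it before the next dose. The laboratory stopping criteria in 8.3.2 (neutrophils, platelets, transaminases with bilirubin) have hematology and chemistry marked in Table 3 at Days 7 and 14. Pregnancy has its own row in Table 3 but no mark at either visit. Two of the three doses are therefore given with no pregnancy test scheduled since Day 0.

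At stake is avoidable exposure of an early pregnancy to a second or third dose. The efficacy and safety analyses do not depend on it.

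**Working it through.** The documents give no figure to reproduce. The check is a reading of the schedule, then day arithmetic.

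**Schedule.** Table 3, pregnancy row against dosing row:

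| Visit day | Dose | Pregnancy test |
|---|---|---|
| Screening | no | serum |
| 0 | dose 1 | urine |
| 7 (4-10) | dose 2 | none |
| 14 (11-17) | dose 3 | none |
| 28, 42 | no | none |
| 56 (53-59) | no | urine |

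Scheduled tests after Day 0 and up to the last dose: 0. Doses given in that interval: 2 of 3. From last dose to next test: 56 - 14 = 42 days nominally, 53 - 17 = 36 at least, 59 - 11 = 48 at most.

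**What added tests would reach.** Let L be the lag in days from conception to a positive urine test. The latest conception a test can detect is the test day minus L. L is not in the documents; 10 to 21 days is assumed.

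| Test | L = 10 | L = 21 |
|---|---|---|
| Day 0 | Day -10 | Day -21 |
| Day 7 (proposed) | Day -3 | Day -14 |
| Day 14 (proposed) | Day +4 | Day -7 |
| Day 56 (existing) | Day +46 | Day +35 |

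With the visit windows, the Day 7 test reaches from 10 - 10 = Day 0 to 4 - 21 = Day -17, and the Day 14 test from 17 - 10 = Day +7 to 11 - 21 = Day -10.

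For any fixed L, the two tests bring 14 further days of conceptions into view before dose 3, and the Day 7 test brings 7 of those into view before dose 2. All of them lie within reach of the Day 56 test: even at its earliest (Day 53) with L = 21, that test reaches Day +32, beyond the latest added conception (Day +7). The added tests bring detection forward; they do not add detections.

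**Size.** Assumptions, none in the documents: 1-10% pregnancies per woman-year on contraception, and 20-50% of the planned 36 being women of reproductive potential (7 to 18). Exposure time is 14/365 = 0.0384 year.

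- Low: 0.0384 x 0.01 x 7 = 0.003 pregnancies per trial detected before dose 3.
- High: 0.0384 x 0.10 x 18 = 0.07.

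**Which test matters more.** Count doses spared times conception-days. Both tests: 7 x 2 + 7 x 1 = 21. Day 14 alone: 14 x 1 = 14. Day 7 alone: 7 x 2 = 14. Either single test gives 14/21, two thirds of the gain in doses. Day 14 alone detects twice as many pregnancies before dosing ends (14 conception-days against 7), which is the reason to put it first.

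**The case against.** The strongest reply is that nothing is broken. Protocol and SAP agree on the same three visits, and no document requires a test before each dose. The stopping rule acts on evidence from any source: anaphylaxis, malignancy and opportunistic infection are on the same list with no scheduled test of their own, and adverse events are reviewed at Days 7 and 14. Contraception is required, a serum and a urine test precede dose 1, dosing lasts 14 days, and the half-life at 8 mg is about 16 minutes (Protocol 5.3). The documents describe no reproductive hazard, and the 120-day reporting period is surveillance that also covers partners of male participants.

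Most of this stands, and it is why the point is minor. It shrinks the gain without removing it. The protocol does not treat contraception as sufficient, since it tests again at Day 0. Nor does fast clearance make later doses irrelevant: Protocol 7.8.2 bases the regimen on an effect lasting 14 days after a single dose in mice.

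Three stronger readings are tempting, and the documents do not support them. A reader might infer that the stopping rule cannot operate during dosing; a report or an unscheduled test can still trigger it. A reader might take the Table 3 note to mean every later visit and see a contradiction with the SAP; the row's dashes and the SAP's explicit list show that it means Day 0 and Day 56. A reader might expect the added tests to find pregnancies that would otherwise be missed; under the assumed lag, the Day 56 test reaches all of them, only later.

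**Conclusion.** The gap is real and minor. After Day 0 there is no scheduled test until Day 56, so no scheduled test after Day 0 can stop dose 2 or dose 3. Closing it would bring about 0.003 to 0.07 detections per trial forward to before dose 3; the Day 56 test could otherwise make them only after dosing. That range rests wholly on the assumed pregnancy rate and number of women, and on a fixed detection lag. The schedule reading rests on none of these. An added test spares later doses only; dose 1 will already have been given. This is a design improvement rather than an inconsistency between the documents.

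**What to change.** Add a predose urine pregnancy test at Day 14, and also at Day 7, for women of reproductive potential. If only one is added, make it Day 14. Use the urine already collected for urinalysis, and state that it is taken before dosing, because Table 3 gives no such timing for that sample. Mark the visits in Table 3, in the SAP's copy of the schedule and in the pregnancy visit list in SAP 7.8.

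On a positive result, withhold the dose. If serum confirmation is wanted before permanent discontinuation, amend 8.3.2 (which has no confirmation step), 12.5 and the Table 3 note (which both specify urine after screening), and the matching SAP wording. If the serum test is negative, dose within the ±3-day window. If confirmation cannot be had in that window, discontinue treatment; this also settles the ban on skipped doses in 8.3.3.

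Cost: no new visit and no routine blood sample. Two urine tests per woman come to 2 x 7 = 14 up to 2 x 18 = 36 on the assumed share, and at most 2 x 50 = 100 if all of up to 50 enrolled were randomized women of reproductive potential. Day 14 alone halves this. An occasional false positive could delay a dose or lead to a replacement under 8.3.4.

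One detail to settle: the SAP 7.8 urinalysis list ends "Crystals, Protein, White blood cells, Yeast. Visits include screening, Day 0, Day 7, Day 56", leaving out Day 14, although Table 3 and the SAP's copy mark it. If urine were not taken on Day 14, one extra sample would be needed.

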8. SELECTION AND WITHDRAWAL OF PARTICIPANTS

8.1. Participant Inclusion Criteria

A participant must meet the following criteria to be eligible for inclusion in the study:

1. Age 18 to 75 years old, inclusive, at the time of signing the informed consent form.
2. Documented diagnosis of EoE by endoscopy prior to screening.
Note: Must include a demonstration of intraepithelial eosinophilic infiltration (peak cell count ≥ 15 eos/hpf [400 \times]) from esophageal biopsy specimens from endoscopy.
3. History (by participant report) of on average at least 2 episodes of dysphagia (with intake of solids off anti-inflammatory therapy) per week in the 4 weeks prior to screening, and on average at least 2 episodes of documented dysphagia per week during any 2 consecutive weeks (qualifying period) between screening and baseline; dysphagia is defined as trouble swallowing solid food, or having solid food stick, by participant report; and completed the DSQ on $\geq 70\%$ of days during the qualifying period prior to baseline (Visit 1).
4. Must remain on a stabilized diet for at least 6 weeks prior to screening and during the course of the study; stable diet is defined as no initiation of single or multiple elimination diets or reintroduction of previously eliminated food groups.
5. Must be willing and able to continue any dietary therapy and/or medical regimens (including gastric acid suppression) in effect at the screening visit. There should be no change to these regimens during the study participation.
6. Willing and able to comply with all clinic visits and study-related procedures.
7. Able to understand and complete study-related questionnaires.
8. Provide signed informed consent.
9. Esophagogastroduodenoscopy (EGD) with photographs performed at screening (qualifying EGD), with a demonstration of intraepithelial eosinophilic infiltration (peak cell count ≥ 15 eos/hpf) in at least 2 of the 3 biopsied esophageal regions (proximal, mid, or distal).

